6.2. Discussion of Study Design

Chronic pain may result from a number of different conditions with different underlying etiologies; however, to increase sensitivity of the study, eligible subjects will be subjects with moderate to severe CLBP who require ATC opioid treatment. The design selected to meet the objectives of the study is a 12-week randomized, double-blind, placebo-controlled, EEW study in subjects with moderate to severe CLBP that requires continuous, ATC opioid treatment and, despite prior dose escalation, did not receive adequate pain relief.

The overall design is consistent with previous studies of modified-release opioid analgesics, Initiative on Methods, Measurement, and Pain Assessment in Clinical Trials (IMMPACT) recommendations (Weaver and Schnoll, 2002; Yarlus et al, 2013 and Dworkin et al, 2005), and the FDA Guidance for Industry – *Analgesic Indications: Developing Drug and Biological Products* (2014) (Dworkin et al, 2008). The Double-Blind Phase will be 12 weeks in duration, which is consistent with FDA guidance and previous studies demonstrating efficacy of opioid formulations. The frequency of visits is considered to be adequate for dosing, monitoring subject’s compliance with study requirements, and not overly burdensome for subjects.

CAM2038 is being evaluated for the management of pain severe enough to require daily, ATC, long-term opioid treatment and for which alternative treatment options are inadequate. Two dosage formulations are being studied (4 mg, 8 mg and 12 mg q1w) and (16 mg, 24 mg and 32 mg q4w).

The study will utilize an EEW approach as an enrichment strategy to enhance the probability of including “responders” and to minimize early discontinuations due to AEs (Dworkin et al, 2012 and FDA CDER, 2014). According to FDA guidance (2014), an enrichment design may be particularly well suited for demonstrating efficacy of alternative dosage forms of an established analgesic. In addition, according to FDA guidance, the titrate-to-effect design may improve subject retention and provide a more realistic picture of efficacy and safety (Dworkin et al, 2012). The use of fixed opioid doses may permit a more rigorous assessment of dose-response, but the limited number of doses may reduce success of the trial, as they are not optimized to meet the subjects’ needs.

During the Titration Phase, subjects will be dosed with CAM2038 q1w until a stabilized dose and adequate analgesic effect has been achieved for at least 2 consecutive weeks prior to randomization to the Double-Blind Phase, in accordance with pre-defined randomization criteria. Subjects whose pain is controlled on 4 mg, 8 mg or 12 mg CAM2038 q1w during the Titration Phase, will be maintained on 4 mg, 8 or 12 mg CAM2038 q1w, or corresponding placebo during the Double-Blind Phase. Subjects whose pain is controlled on 16 mg CAM2038 q1w or higher during the Titration Phase will be transitioned to CAM2038 q4w/placebo during the Double- Blind Phase.

Although there are inherent differences in the PK profiles for weekly and monthly administered products, the CAM2038 q1w and q4w formulations are similar with respect to steady state maximum plasma concentration and trough plasma concentration of BPN. Based on these similarities, the CAM2038 products are expected to be interchangeable when subjects go from weekly to monthly dosing regimens.

Rescue medication, hydrocodone/acetaminophen 5 mg/325 mg, will be provided to help minimize opioid withdrawal symptoms in subjects during the Titration Phase and the Double-Blind Phase (particularly in subjects randomized to placebo). Randomization will be used to avoid bias in the assignment of subjects to treatment, to increase the likelihood that known and unknown subject attributes (e.g., demographics and baseline characteristics) are evenly balanced across treatment groups, and to enhance the validity of statistical comparisons across treatment groups.

A placebo control will be used to establish the frequency and magnitude of changes in clinical endpoints that may occur in the absence of active treatment, as well as to minimize subject and investigator bias. Double-blinded treatment in the Double-Blind Phase will be used to reduce potential bias of subjects and investigators during data collection and evaluation of clinical endpoints.

During the Double-Blind Phase, the pharmacist will be unblinded to the randomization code to permit dispensation of the CAM2038 or placebo q1w and CAM2038 or placebo q4w syringes to an unblinded staff member who will perform the injections. All other site study personnel, including the investigator and study coordinator, as well as the subjects, will remain blinded to treatment during the Double-Blind Phase of the study. The unblinded staff member will be instructed not to discuss the trial with the blinded staff to ensure the blind is maintained.

The opening of recruitment of subjects for the safety extension is to ensure that a sufficient number of subjects are enrolled to provide required long-term safety data to support the clinical development of CAM2038 for the indication of chronic pain requiring daily treatment with opioids.

7. SELECTION OF STUDY POPULATION

Approximately 875 subjects will be screened to obtain approximately 340 randomized subjects (170 subjects per treatment group). The study comprises two treatment arms: a group of approximately 170 subjects receiving SC CAM2038 q1w or CAM2038 q4w and a group of approximately 170 subjects receiving SC placebo q1w or q4w. Approximately 85 study sites in the United States will be utilized.

Subjects who discontinue prematurely may be replaced at the discretion of the Medical Monitor and the Principal Investigator, in order to maintain study power.

The study population will consist of adult males and females with moderate to severe CLBP currently requiring treatment with daily opioids ≥ 40 mg MED.

For the extension phase, approximately 140 subjects will be enrolled to obtain 100 completed subjects.

7.1. Inclusion Criteria

Subjects must meet all of the following inclusion criteria in order to be eligible for participation in the study:

1. Written informed consent provided prior to the conduct of any study-related procedures.
2. Male or non-pregnant, non-lactating female subject, greater than or equal to 18 years old.
3. Body mass index (BMI) between 18 and 38 kg/m², inclusive.
4. Treated with daily opioids for moderate to severe CLBP for a minimum of 3 months prior to Screening.
5. On a stable dose of ≥ 40 mg/day of oral morphine or MED during the 14 days prior to Screening.
6. Systolic blood pressure ≥ 100 mmHg and diastolic blood pressure ≥ 60 mmHg.
7. Female subject of childbearing potential who is willing to use a reliable method of contraception during the entire study (Screening Visit to final Follow-up; see Section 9.1.5). To be considered not of childbearing potential, female subjects must be surgically sterile (hysterectomy or bilateral oophorectomy, or bilateral tubal ligation with surgery at least 6 weeks before Screening).
8. Male subject who is willing to use reliable contraception.
9. Willing and able to comply with all study procedures and requirements.

7.2. Exclusion Criteria

Subjects will not be eligible for participation in the study if any of the following exclusion criteria are met:

1. Positive for hepatitis B surface antigen, hepatitis C RNA, or antibodies to human immunodeficiency virus (HIV).

2. Clinically significant symptoms, medical conditions, or other circumstances which, in the opinion of the investigator, would preclude compliance with the protocol, adequate cooperation in the study, or obtaining informed consent, or may prevent the subject from safely participating in the study, including the following:
 - a) Severe respiratory insufficiency, respiratory depression, airway obstruction, gastrointestinal motility disorders, biliary tract disease, severe hepatic insufficiency, or planned surgery.
 - b) Bipolar disorder
3. Current diagnosis of Diagnostic and Statistical Manual of Mental Disorders, Fifth Edition– defined moderate to severe substance use disorder (including alcohol), other than caffeine or nicotine.
4. Female subject planning to become pregnant during the study.
5. Surgical procedure(s) for CLBP within 6 months prior to Screening.
6. Concomitant disease(s) that could prolong the QTcF interval, such as autonomic neuropathy (caused by diabetes or Parkinson’s disease), HIV, cirrhosis, Long QT Syndrome, or family history of Long QT Syndrome.
7. QTcF >450 ms for males and >470 ms for females, or clinically significant electrocardiogram (ECG) abnormality at Screening, at the investigator’s discretion.
8. Currently taking medications that have the potential to prolong the QTcF interval or may require such medications during the course of the study ([Appendix 1](#)) and has clinically significant abnormalities on screening ECG readings, as determined by the investigator.
9. A nerve or plexus block, including epidural steroid injections or facet blocks, within 1 month prior to Screening or botulinum toxin injection in the lower back region within 3 months of Screening.
10. History of chemotherapy or confirmed malignancy (except basal cell carcinoma) within the past 2 years.
11. Any other acute or chronic pain condition that could interfere with the subject’s ability to report their CLBP accurately and consistently and/or interfere with the study staff’s ability to assess the subjects CLBP.
12. An active or pending workman’s compensation, insurance claim, or litigation related to back pain (i.e., primary claim is back pain).
13. Clinically significant history, in the opinion of the investigator, of suicidal ideation or current evidence that the subject is actively suicidal.
14. Clinically significant history of major depressive disorder that is poorly controlled with medication, per investigator judgment.
15. Hypersensitivity or allergy to BPN, other opioids, or excipients of CAM2038.
16. Hypersensitivity or allergy to acetaminophen.
17. Use of strong inhibitors or inducers of cytochrome P450 3A4 (CYP3A4), such as some azole antifungals (e.g., ketoconazole), macrolide antibiotics (e.g., clarithromycin), or protease inhibitors

- (e.g., ritonavir, indinavir, and saquinavir) within the 30 days prior to Screening,
18. Use or planned use of natural supplements that can affect CYP3A4, such as St. John's Wort, throughout the study.
 19. Has a major bleeding disorder, such as hemophilia, or treated with high levels of anticoagulants per the investigator's discretion
 20. Current or confirmed past diagnosis of Sphincter of Oddi dysfunction.
 21. Has a significant hepatic disease, as indicated by Screening clinical laboratory assessment results (aspartate aminotransferase, alanine aminotransferase, or lactate dehydrogenase values $\geq 3 \times$ the upper limit of normal [ULN]) or has a creatinine value $> 1.5 \times$ ULN).
 22. Is an employee of the investigator or the trial site, with direct involvement in the proposed trial or other studies under the direction of the investigator or trial site or is a family member of the investigator or of an employee of the investigator.
 23. Has any pending legal action that could prohibit participation or compliance in the study.

7.3. Criteria for Entry into the Open-Label Titration Phase

In order to be entered into the Titration Phase, subjects must meet the following criteria:

1. After at least a 12-hour washout from the last IR morphine dose, subject must have a COWS ≥ 5 and an API pain score over the past 24 hours ≥ 5 in order to receive a test dose of Buprenex.
2. Passed all baseline criteria, including a normal QTcF, had no change in QTcF > 30 ms at 1 hour after the test dose with Buprenex, and had a COWS score > 5 after the test dose with Buprenex.

Note:

- Subjects on BPN at Screening are required to participate in the down titration and will undergo a washout period prior to the test dose and first on-study treatment. Subjects entering the study on BPN will not transition to IR Morphine, but will refrain from taking their BPN for 12 -24 hours prior to the test dose to achieve the desired washout period.
- Subjects on BPN at Screening are still required to follow the same Day 1 procedures (e.g., confirmation of pain scores, COWS assessment and Buprenex test dose) as non-BPN subjects.

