Subjects who were previously on BPN prior to Screening will not need to participate in the morphine IR phase. However, subjects who were previously on BPN will be required to refrain from taking BPN for 12-24 hours as a washout prior to starting open label titration on CAM2038.

Following the morphine IR treatment, subjects will enter the Titration Phase. On Day 1 of the Titration Phase, subjects will return to the clinic after a washout of at least 12 hours from their last morphine IR dose, or 12-24 hours from their last BPN dose. Subjects who report a CLBP of ≥ 5 on the API scale and have a Clinical Opiate Withdrawal Scale (COWS) score of ≥ 5 , will receive a BPN test dose (Buprenex[®] 0.30 mg intramuscular [IM] injection) at the clinical site. After the Buprenex test dose, subjects will be assessed for any changes in QTcF (Fridericia’s corrected QTc) and withdrawal. Subjects who tolerate the BPN test dose, do not show an increase >30 ms in

QTcF within 1 hour after the test dose, and have a COWS score of <5 within 15 minutes after the test dose will receive the first dose of SC CAM2038 q1w within 4 hours (+30 minutes) after the test dose (4 mg CAM2038 for subjects whose screening MED was between 40 mg/day and 79 mg/day; and 8 mg CAM2038 for subjects whose screening MED was ≥ 80 mg/day).

During the first week of the Titration Phase, subjects who experience significant pain may, at the discretion of the investigator, receive an additional dose at their corresponding CAM2038 q1w dosing level (4 mg or 8 mg respectively) on Day 3, 4 or 5. Subjects will then attend clinic visits every week for dosage adjustment. Dose adjustments will be made by increasing the dose level of CAM2038 q1w at the scheduled weekly visits (doses of 4 mg, 8 mg, 12 mg, 16 mg, 24 mg, or 32 mg per week). Subjects who require doses >32 mg/week will be discontinued from the study.

Rescue medication, consisting of hydrocodone/acetaminophen 5 mg/325 mg every 4 to 6 hours (q4-6h), may be taken during the Titration Phase as needed (prn), up to 15 mg/975 mg/day (3 tablets) for subjects whose MED at screening was 40-79 mg/day or up to 30 mg/1950 mg/day (6 tablets) for subjects whose MED at screening was ≥ 80 mg/day). The goal of the Titration Phase is to reach a stable dose of CAM2038 q1w that produces analgesia, by the end of the 10-week period.

Eligible subjects will receive CAM2038 titrated to a dose that meets the following criteria:

- Provides analgesia (i.e., 7-day mean API ≤ 4)

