1. After at least a 12-hour washout from the last IR morphine dose, subject must have a COWS ≥ 5 and an API pain score over the past 24 hours ≥ 5 in order to receive a test dose of Buprenex.
2. Passed all baseline criteria, including a normal QTcF, had no change in QTcF > 30 ms at 1 hour after the test dose with Buprenex, and had a COWS score < 5 after the test dose with Buprenex.

Note:

- Subjects on BPN at Screening are required to participate in the down titration and will undergo a washout period prior to the test dose and first on-study treatment. Subjects entering the study on BPN will not transition to IR Morphine, but will refrain from taking their BPN for 12 -24 hours prior to the test dose to achieve the desired washout period.
- Subjects on BPN at Screening are still required to follow the same Day 1 procedures (e.g., confirmation of pain scores, COWS assessment and Buprenex test dose) as non-BPN subjects.

Criteria for Randomization into the Double-Blind Phase:

1. Been on a stable dose of CAM2038 q1w for at least 2 consecutive weeks.
2. CAM2038 titrated to a dose that provides analgesia (i.e., 7-day API score of ≤ 4 and at least 2 points below the value at the start of Titration Phase) and is well tolerated for 7 days before randomization.
3. Requires no more than an average of one hydrocodone/acetaminophen 5 mg/325 mg/day during the last 7 days prior to randomization.
4. Demonstrated study medication (CAM2038) compliance $\geq 80\%$ during the previous 14 days.
5. Demonstrated daily compliance with pain intensity scoring for ≥ 11 of the previous 14 days, including the last 3 days prior to randomization.

Inclusion Criteria for Open Label Extension

For Subjects Continuing from The Randomized Double-Blind Phase.

Subjects must have:

1. Completed Double Blind Phase of the study
2. Signed Informed Consent for Safety Extension

Subjects completing the double-blind phase will be enrolled directly into the open label extension at their respective dose level of CAM2038. They will not be required to participate in a Buprenex treatment test dosing or participate in a titration phase.

For De Novo Subjects (New Subjects Recruited Directly into The Open Label Extension)

Subjects who are not participating in the Double-Blind Phase of the Study must meet all of the following inclusion criteria in order to be eligible for participation in the study:

1. Written informed consent provided prior to the conduct of any study-related procedures.

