2. Male or non-pregnant and non-lactating female subject, greater than or equal to 18 years old.
3. BMI between 18 and 38 kg/m², inclusive.
4. Treated with daily opioids for moderate to severe chronic pain disorder such as CLBP or osteoarthritis for a minimum of 3 months prior to Screening.
5. On a stable dose of >40 mg/day of oral morphine or MED during the 14 days prior to Screening.
6. Systolic blood pressure \geq 100 mmHg and diastolic blood pressure \geq 60 mmHg.
7. Female subject of childbearing potential who is willing to use a reliable method of contraception during the entire study (Screening Visit to final Follow-up). To be considered not of childbearing potential, female subjects must be surgically sterile (hysterectomy or bilateral oophorectomy, or bilateral tubal ligation with surgery at least 6 weeks before Screening).
8. Male subject who is willing to use reliable contraception
9. Willing and able to comply with all study procedures and requirements.

Exclusion Criteria for Subjects Continuing from The Randomized Double-Blind Phase

1. Clinically significant symptoms, medical conditions, or other circumstances which, in the opinion of the investigator, would preclude compliance with the protocol, adequate cooperation in the study, or obtaining informed consent, or may prevent the subject from safely participating in the study.

Exclusion Criteria for De Novo Subjects only:

Same exclusion criteria as for subjects participating in the Randomized Double-Blind Treatment Phase.

Criteria for Entry into the Titration Phase (for De novo subjects):

1. After at least a 12-hour washout from the last IR morphine dose, subject should have a COWS \geq 5 and an API pain score over the past 24 hours \geq 5 in order to receive a test dose of Buprenex.
2. Passed all baseline criteria, including a normal QTcF, had no change in QTcF >30 ms at 1 hour after the test dose with Buprenex, and had a COWS score <5 after the test dose with Buprenex.

Note:

- Subjects on BPN at Screening are required to participate in the down titration and will undergo a washout period prior to the test dose and first on-study treatment. Subjects entering the study on BPN will not transition to IR Morphine, but will refrain from taking their BPN for 12 -24 hours prior to the test dose to achieve the desired washout period.

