8.1.3. Titration Phase

After administration of the Buprenex test dose on Day 1, subjects who tolerate the test dose, do not show an increase of > 30 ms in QTcF within 1 hour, and have a COWS score of < 5 within 15 minutes after the test dose will receive their first dose of CAM2038 q1w within 4 hours (+ 30 minutes) after the test dose. Subjects whose screening opioid dose was between 40 mg and 79 mg/day MED will be started on 4 mg CAM2038 q1w. Subjects whose screening opioid dose was ≥ 80 mg/day MED will be started on 8 mg CAM2038 q1w. During the first week of the Titration Phase, subjects who experience significant pain may, at the discretion of the investigator receive a second dose of CAM2038 at their respective dose (4 mg for subjects whose screening MED was 40-79 mg/day; 4 or 8 mg CAM2038 q1w for subjects whose screening Med was ≥ 80 mg/day) on Day 3, 4, or 5. Subjects will then attend clinic visits every week for dosage adjustment. Dose adjustments will be made by increasing or decreasing the dose level of CAM2038 q1w at the scheduled weekly visits (doses of 4 mg, 8 mg, 12 mg, 16 mg, 24 mg, or 32 mg per week).

The maximum dose within a 7-day period cannot exceed 32 mg. Subjects who require doses higher than 32 mg/week will be discontinued from the study. The dosing of CAM2038 q1w will be titrated with the purpose of achieving a stable dose of CAM2038 q1w by the end of the 10-week Titration Phase.

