9. STUDY PROCEDURES AND ASSESSMENTS

All study assessments will be performed at the visits and time points outlined in the Schedule of Assessments ([Table 5](#), [Table 6](#), and [Table 7](#)). Open-label safety extension assessments for existing subjects enrolled from the randomized Double-Blind Phase is present in [Table 8](#). [Table 9](#) and [Table 10](#) presents the schedule of assessments for de novo subjects in Open Label Safety Extension Phase. The following sections outline the details and procedures associated with the assessments.

Table 5: Schedule of Assessments for Screening, Transition, and Titration Phases

Study Period/Phase:	Screening	Transition Phase ¹		Open-Label Titration Phase ²									
	Week: W-2 to -1	W0		W1	W2	W3	W4	W5	W6	W7	W8	W9	W10
Day:	D-14 to -1	D1 up to 10-12 days ³	2 to 4 days										
Informed Consent ⁴	X												
Eligibility Criteria Review	X			X ⁵									
Demographic Data	X												
Medical and Medication History	X												
Physical Examination ⁶	X												
Vital Signs ⁷	X			X ⁸	X	X	X	X	X	X	X	X	X
ECG	X			X ^h	X	X	X	X	X	X	X	X	X
Clinical Laboratory Assessments	X			X				X ⁹					
Pregnancy Test ¹⁰	X			X		X		X		X		X	
Hepatitis B/C, HIV ¹¹	X												
Urine Drug Screen	X			X	X	X	X	X	X	X	X	X	X
Dispense Treatment Identification Card				X									
Down-Titrate Opioid Dose		X											

¹ Subjects on BPN at screening will participate in the down titration but will not transition to morphine IR. Subjects will washout and refrain from their BPN treatment for 12-24 hours prior to the test dose on Day 1.

² Titration Phase visit window is ±3 days.

³ Telephone contact.

⁴ Subjects must voluntarily provide written informed consent prior to any study-related procedures being performed.

⁵ Prior to starting the Titration Phase, all Inclusion/Exclusion and other relevant criteria must be met.

⁶ A complete physical examination of all major body systems (including height, weight, and BMI) will be performed.

⁷ Includes body temperature, blood pressure, pulse rate, pulse oximetry and respiration rate.

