9.2. Eligibility Review and Randomization

At the Screening Visit, the investigator or designee must document that the subject meets all inclusion and no exclusion criteria via a signed note or eligibility and clinical stability checklist. In addition, subjects must fulfill the criteria for entry into the Transition Phase, the Titration Phase, the Double-Blind Phase and the Open Label Safety Extension Phase. Randomization will be accomplished centrally using an Interactive Response Technology managed by the Sponsor.

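### Protocol Section 7.3 reverses the COWS threshold after the test dose: it requires a score above 5 to enter titration, where every other statement requires below 5

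*Protocol*

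**What the plan says.** Protocol Section 7.3 sets two conditions for entering the Titration Phase. Item 1 applies before the Buprenex test dose: after washout the subject needs a COWS of at least 5 and an average pain score of at least 5. Item 2 applies afterwards. Besides its QTcF conditions, it requires that the subject "had a COWS score > 5 after the test dose with Buprenex".

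The synopsis, under the titration entry criteria for the core study, gives item 2 in matching terms but says the subject "had a COWS score < 5 after the test dose with Buprenex". Section 8.1.3, which governs the first depot injection, gives it to subjects who tolerate the test dose, stay within the QTcF limit and "have a COWS score of < 5 within 15 minutes after the test dose".

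Two other places make the titration entry criteria binding. Section 9.2 states that "subjects must fulfill the criteria for entry into the Transition Phase, the Titration Phase, the Double-Blind Phase" and the extension phase. A footnote to Table 5 says: "Prior to starting the Titration Phase, all Inclusion/Exclusion and other relevant criteria must be met".

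**The concern.** The sequence on Day 1 of titration is meant to show that a subject in opioid withdrawal is relieved by buprenorphine before being given a depot that cannot be withdrawn. A subject arrives with a COWS of 5 or more, receives the short-acting test dose, and goes on only if it is tolerated and the score falls below 5. Item 2 of Section 7.3 asks for the reverse: the score must still exceed 5 after the dose.

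Eligibility is audited against the written criteria, and Section 7.3 is where those criteria are listed for the core study. A checklist or programmed check built from that section would carry the wrong sign. It would fail correctly dosed subjects and pass anyone dosed while still in withdrawal. SAP Section 11 plans a summary of major deviations from entry criteria drawn from coded data, and SAP Section 5.3 removes major violators from the Per Protocol Population, so a wrong sign could reach both.

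**Working it through.** No calculation in the plan depends on this threshold. The check is a comparison of every statement in the protocol of a COWS cut-off after the test dose. The SAP gives none.

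| Place in the protocol | Subjects | Wording | Sign |
|---|---|---|---|
| Section 7.3, item 2 | Core | "had a COWS score > 5 after the test dose with Buprenex" | > 5 |
| Synopsis, Methodology | Core | "have a COWS score of <5 within 15 minutes after the test dose will receive the first dose of SC CAM2038 q1w" | < 5 |
| Synopsis, titration entry criteria | Core | "had a COWS score < 5 after the test dose with Buprenex" | < 5 |
| Synopsis, de novo titration entry criteria | De novo | "had a COWS score <5 after the test dose with Buprenex" | < 5 |
| Section 6.1.2 | Core | "have a COWS score of <5 within 15 minutes after the test dose" | < 5 |
| Section 7.6.3, item 2 | De novo | "had a COWS score <5 after the test dose with Buprenex" | < 5 |
| Section 8.1.3 | Core | "have a COWS score of < 5 within 15 minutes after the test dose" | < 5 |

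Count: 1 + 6 = 7 statements, one with > 5 and six with < 5. Leaving out the two de novo statements, the core-study comparison is one against four.

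**Could the statements be reconciled?**

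- As a pre-dose rule: no. Item 1 of Section 7.3 already sets that rule at 5 or more, and item 2 refers expressly to the time after the test dose. The cut-offs of 5 or more in the schedule footnotes also belong to the pre-dose assessment.
- As a rule for a different group: no. Four of the < 5 statements apply to the same core subjects, and the de novo criteria use < 5 as well.
- Through a statement elsewhere: no. Section 8.1.2 gives the timing of the post-dose COWS (15 minutes) but no cut-off.

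**What each section admits.** Take illustrative subjects with a pre-dose COWS of 8, which passes the requirement of 5 or more, and three possible post-dose scores:

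| Post-dose COWS | Section 7.3 as written (> 5) | Section 8.1.3 (< 5) | Section 7.3 corrected (< 5) |
|---|---|---|---|
| 3 | fails | passes | passes |
| 5 | fails | fails | fails |
| 8 | passes | fails | fails |

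No score is both above 5 and below 5, so no subject can meet Sections 7.3 and 8.1.3 together. With the sign corrected the two sections agree at every score, including exactly 5.

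**The case against.** The strongest reply is that this is a one-character slip which the surrounding text resolves. The section that governs dosing is correct, as are the synopsis and the design narrative. A site applying Sections 7.3 and 8.1.3 together could dose nobody and would notice at its first subject. That stands, and it is why misdosing is unlikely. But obvious intent shows only which sign is right. It does not remove the contradiction from the formal criteria list.

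The text was read from PDF by a program, so a misread character cannot be fully excluded. That also stands. The mismatch is certain in the text as supplied, but the source file should be checked before anything is issued.

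The route to harm is not documented. Section 9.2 mentions a checklist for screening eligibility, and neither it nor the Table 5 footnote cites Section 7.3. The Protocol Deviation Plan is not among the documents. A wrong sign in an operational tool is therefore a risk to rule out, not a shown effect.

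Two of the six comparison statements concern de novo subjects. That is fair, but the four core-study statements settle the point alone.

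Finally, the fix may come late. The SAP was finalised on 31 August 2018, and once double-blind enrolment closes, new entrants to titration come under Section 7.6.3, which is correct. The status of core titration is not stated. If it is over, correcting the protocol matters less, while checking how subjects were classified still matters.

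**Conclusion.** The concern holds. Section 7.3 item 2 states the post-test-dose COWS threshold with the wrong sign. It disagrees with all six other statements and is incompatible with the dosing rule in Section 8.1.3. This rests on the supplied text being a faithful reading of the protocol.

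The consequence is confined to eligibility and safety documentation. Section 7.4 does not use COWS for randomisation, and the primary analysis uses the mITT Population, so sample size, power, alpha and the primary comparison do not change. The documents do not show how many subjects, if any, were handled under the wrong sign. It should be fixed because the criterion controls the first depot injection and the correction is exact.

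**What to change.** Check the source file. If it carries the same sign, change item 2 of Section 7.3 to require a COWS score below 5 after the test dose, matching the synopsis. A score of exactly 5 is then excluded, as it is under Section 8.1.3, so no further rule is needed. Confirm that the eligibility checklist and any programmed deviation checks use below 5. If any were built with the reversed sign, correct them and review the affected classifications before the deviation summary and the Per Protocol Population are produced.

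The cost is one character, by clarification letter or in the next minor amendment, plus a short check of the checklist and the deviation specification. No analysis needs redesign.
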